Appendix A. Analytical Study Week Assignments

Selected endpoints will be summarized by scheduled study visits in descriptive analyses. Since the actual visits may not exactly coincide with their scheduled visit day, the actual visit day is mapped to the study visit generally by non-overlapping consecutive intervals covering the entire time continuum, with scheduled visit time being the center of each interval. The mapping intervals for all distinct schedules are summarized in the following tables.

Handling multiple records assigned to an analytical study week:

If there is more than one record in a study week interval, the analytical record for that specific study week will be defined as the record closest to the scheduled study day of that specific study week ($7 \times \text{study week} + 1$). If two records are equidistant from the scheduled day, then the earlier record will be chosen. If there are multiple records on the same day, the last record will be used.

Scheduled Visit Week	Target Study Day	Vital Signs, Lipids, Chemistry	Physical Measurements
Week 0	1	≤ 1	≤ 1
Week 4	29	(1, 56]	NA
Week 12	85	(56, 126]	NA
Week 24	169	(126, 210]	NA
Week 36	253	(210, 294]	NA
Week 48	337	(294, 350]	NA
Week 52	365	(350, 448]	(1, 546]
Week 76	533	(448, 630]	NA
Week 104	729	> 630	> 546

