6.1.4.1 Elevation of Creatine Kinase (CK)

If CK is > 5x ULN, CK must be retested before IP is administered. In addition, investigators will ask study subjects to promptly report muscle pain, soreness, cramps, or weakness especially if accompanied by malaise or fever. If such symptoms occur and no scheduled study laboratory assessments are performed, the subject's CK levels should be measured by unscheduled assessment. If CK is > 5x ULN, the subject must be instructed as soon as possible to discontinue statin, other applicable lipid background therapy, and/or Amgen IP (evolocumab). CK must be retested before statin, other lipid background therapy, and/or IP (evolocumab) administration can be continued. A sample for urinalysis must be collected and sent to the central laboratory if CK is elevated > 10x ULN on retest as per table below.

The following rules apply for scheduled laboratory assessments and for unscheduled CK measurements:

CK at scheduled or unscheduled visit	CK on retest	Investigational Product and/or Statin and/or other lipid lowering therapies Administration
> 5x ULN	> 10x ULN	Discontinue both statin, other lipid lowering therapies, and IP ^a . Collect urine sample for urinalysis. Contact Amgen Medical Monitor.
	> 5x to ≤ 10x ULN	Discontinue statin, other lipid lowering therapies, and retest CK before administration. Consider continuing IP if alternative explanation.
	≤ 5x ULN	Consider continuing statin, other lipid lowering therapies and IP

^a CK elevations >10x ULN that have been confirmed to be secondary to myocardial infarction do not require discontinuation of statin, other lipid lowering therapy or IP

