14. APPENDICES

Appendix A. Additional Safety Assessment Information

Adverse Event Toxicity Grading Scale

Refer to the NCI Common Terminology Criteria for AEs (CTCAE) Version 4.0 for AE grading and information. The CTCAE is available at the following link:

http://ctep.cancer.gov/protocolDevelopment/electronic_applications/ctc.htm.

When an AE cannot be graded by CTCAE v4.0 the following severity grade may be used:

Grade	Amgen Standard Adverse Event Severity Scoring System
1	MILD: Aware of sign or symptom, but easily tolerated
2	MODERATE: Discomfort enough to cause interference with usual activity
3	SEVERE: Incapacitating with inability to work or do usual activity
4	LIFE-THREATENING: Refers to an event in which the patient was, in the view of the investigator, at risk of death at the time of the event. (This category is not to be used for an event that hypothetically might have caused death if it were more severe.)
5	FATAL

Drug-induced Liver Injury Reporting & Additional Assessments

Reporting

To facilitate appropriate monitoring for signals of DILI, cases of concurrent AST/ALT and TBL elevation according to the criteria specified in [Section 6.1.4.2](#) (3x ULN for AST/ALT and 2x ULN for TBL) require the following:

- The event should be reported to Amgen as a serious adverse event within **24 hours** of discovery or notification of the event (ie, before additional etiologic investigations have been concluded)
- The appropriate eCRF (eg, adverse event eCRF) that captures information necessary to facilitate the evaluation of treatment-emergent liver abnormalities should be completed.

Other events of hepatotoxicity and potential DILI should be reported as serious adverse events if they meet the criteria for a serious adverse event defined in [Section 9.2.1](#).

Additional Clinical Assessments and Observation

All subjects in whom IP is withheld due to potential DILI or who experience AST/ALT elevations >3x ULN should undergo a period of “close observation” until abnormalities return to normal or to the subject’s baseline levels. Assessments that should be performed during this period include:

- Repeat liver chemistries within 24-48 hours (ALT, AST, ALP, TBL); in cases of TBL >2x ULN or AST/ALT much greater than 3x ULN, retesting should be performed within 24 hours

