6.3 Other Study Related Definitions

Analytical Study Week Assignments

Analytical windows will be used to assign parameter measurements to study weeks.

The algorithm is provided in [Appendix A](#).

Actual Treatment Group

A subject's actual treatment group in the parent study is the randomized treatment group, unless the subject receives treatment throughout the parent study that is different than the randomized treatment group assignment, in which case the actual treatment group is the treatment received.

Investigational Product (IP)

IP is AMG 145 SC 420 mg QM

IP Exposure Period in Months

IP Exposure Period = [min (Last IP Dose Date + 28 days, EOS Date) - First IP Dose Date +1] / 365.25 * 12

Study Exposure Period in Months

For each randomized subject, Study Exposure Period = (EOS date – Enrollment Date + 1) / 365.25 * 12

Treatment Emergent Adverse Event (TEAE)

Treatment emergent adverse events are adverse events occurring between the first dose of IP and EOS. Treatment emergent adverse events can be identified if answer to the AE eCRF question “Did event start before first dose of investigational product?” is No or missing.

Reflexive Approach for LDL-C and VLDL-C

For all analyses related to LDL-C and VLDL-C, unless specified otherwise, a reflexive approach will be used. When calculated LDL-C is less than 40 mg/dL or triglycerides are > 400 mg/dL, the UC LDL-C and VLDL-C value from the same blood sample will be used instead of calculated LDL-C and VLDL-C, if available.

7. Analysis Subsets

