10.6.3 Laboratory Test Results

Descriptive statistics will be provided for actual values and changes from baseline in select laboratory parameters at each protocol-specified scheduled visit. Laboratory analytes are provided in the protocol Table 1. Lab shift tables using the CTCAE v4.03 grading will be used for the select analytes of interest, when applicable.

In addition, CK and liver function test (LFT) abnormalities will be assessed by the incidence overall and by visits of the following categories:

- CK > 5 x ULN
- CK > 10 x ULN
- ALT or AST > 3 x ULN
- ALT or AST > 5 x ULN
- Total bilirubin \geq 2 x ULN
- (ALT or AST > 3 x ULN) and Total bilirubin > 2 x ULN and ALP < 2 x ULN

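### By-visit CK and liver-test abnormality counts can lose an elevated value to its own retest, because SAP Appendix A keeps only the record nearest the target day

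*SAP*

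**What the plan says.** SAP 6.3 sets the general rule: "Analytical windows will be used to assign parameter measurements to study weeks". The window table in SAP Appendix A has a column headed "Vital Signs, Lipids, Chemistry", so CK, ALT, AST, ALP and bilirubin fall under it. One record survives per window: "the analytical record for that specific study week will be defined as the record closest to the scheduled study day". Two further rules settle the remaining cases: "If two records are equidistant from the scheduled day, then the earlier record will be chosen", and "If there are multiple records on the same day, the last record will be used". Neither section excludes retests or unscheduled samples, and neither gives a worst-value rule.

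SAP 10.6.3 states: "CK and liver function test (LFT) abnormalities will be assessed by the incidence overall and by visits of the following categories". The categories are CK above 5x and 10x ULN, ALT or AST above 3x and 5x ULN, total bilirubin at or above 2x ULN, and a combined row that also requires ALP below 2x ULN. The section does not say which records feed the overall count or the by-visit count.

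The protocol creates extra records when values are high. Section 6.1.4.1 says "If CK is > 5x ULN, CK must be retested before IP is administered", and it asks for an unscheduled CK when muscle symptoms arise without a scheduled laboratory assessment. Section 6.1.4.2 sends any ALT or AST above 3x ULN to close observation. Protocol Appendix A describes that observation as starting with "Repeat liver chemistries within 24-48 hours (ALT, AST, ALP, TBL"), followed by monitoring two or more times a week. Section 7.2.2.5 routes all on-study samples to the central laboratory.

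The only worst-value rule is in Protocol 10.4.2.4, and it concerns the laboratory shift tables.

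**The concern.** Choosing the nearest record is a sound convention for means and changes, where the number of records in a window has little to do with the result. Here it does. The retest triggers (CK above 5x ULN, ALT or AST above 3x ULN) are the same as the lowest CK and ALT/AST categories that SAP 10.6.3 tabulates. Each such abnormality is therefore expected to bring a second record into competition with the first. If the second is lower and nearer the target day, the table shows the subject below threshold at that visit.

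The study's primary objective is safety, and these tables are where muscle and liver laboratory signals are laid out over time. A by-visit row that omits transient elevations because they were followed up gives a misleading picture of when and how often they occurred.

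**Working it through.** No figure in the documents states the size of this effect, so there is none to reproduce. The check applies the Appendix A rule as written.

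**Inputs.** Target days and windows come from SAP Appendix A. The visit window of ±7 days comes from Protocol 7.2.1.1 to 7.2.1.5 and gives 15 possible visit days. The nearest-record, tie and same-day rules are those quoted above. The lag L from visit sample to repeat is an assumption shown as a range. The protocol gives no CK retest interval, and it does not say whether the liver repeat interval runs from the draw or from the result.

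**Condition for displacement.** Let the visit fall v days before target and the repeat L days after the visit. The repeat is nearer when |L − v| < v, that is 0 < L < 2v. At L = 2v the two tie and the earlier record is kept. If the visit is on or after target, a repeat on a later day is never nearer. A same-day repeat always wins, because the last record of the day is used.

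A repeat that displaces the visit value lies within 7 days of target. Every post-baseline window reaches at least 13 days either side of its target (the tightest is Week 48, 350 − 337 = 13). The counts are therefore the same in all eight windows.

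| Lag L (days) | Days early needed | Visit days with displacement |
|---|---|---|
| Same day | any | 15 of 15 |
| 1 | 1 to 7 | 7 of 15 (47%) |
| 2 or 3 | 2 to 7 | 6 of 15 (40%) |
| 4 or 5 | 3 to 7 | 5 of 15 (33%) |
| 6 or 7 | 4 to 7 | 4 of 15 (27%) |
| 10 | 6 or 7 | 2 of 15 |
| 13 | 7 | 1 of 15 |
| 14 or more | none | 0 of 15 |

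With repeated liver testing about twice a week, all later values normal and the first repeat at day 1 or day 2, the result is 7 or 6 of 15.

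**Example (invented values).** Week 12 has target day 85. CK is 12x ULN at a visit on day 80 and 3x ULN on a retest on day 84. The distances are 5 and 1, so the Week 12 record is 3x ULN and neither CK category is met. With the visit on day 85 and the retest on day 87, the elevated value is kept.

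**Second route, with no early visit.** The Week 76 window runs from day 449 to day 630, which is 630 − 448 = 182 days. Fifteen of these lie within 7 days of day 533. If the scheduled visit is in its window and normal, an unscheduled elevation on any of the other 182 − 15 = 167 days is farther from target and is dropped from the by-visit count.

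**Direction.** One record chosen from several cannot exceed their maximum. Against the standard of any value above threshold in the window, each single-analyte by-visit count is equal or too low. This argument does not carry over directly to the combined row, which includes an upper limit on ALP.

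**After the fix.** With the worst value per window, the elevation is lost on 0 of 15 visit days at every lag.

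**The case against.** Several points on the other side stand.

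- **Overall incidence.** A reader might infer that it is understated too. The documents do not support that. SAP 10.6.3 names overall and by-visit incidence as separate outputs, and Appendix A introduces its windows for summaries by scheduled visit. The source of the overall count is unstated, which is a gap and not a demonstrated error.
- **Size.** A reader might take 47% as the share of elevations lost. It is a count of visit days under an assumed even spread, at the shortest next-day lag, and central-laboratory turnaround makes that lag hard to achieve. Dosing is every 4 weeks and the CK retest need only precede dosing, so lags of 14 days or more, with no displacement, are compatible with the text, although Protocol 6.1.4.1 also asks for prompt action. Loss further requires the selected value to be below threshold; a persistent elevation is still counted. No base rate is given, so no number of subjects follows.
- **Other outputs.** The worst-shift tables (Protocol 10.4.2.4), the adverse event tables and the events of interest for muscle and transaminases (SAP 10.6.1) do not depend on this selection. Concurrent transaminase and bilirubin elevation is reported as a serious event (Protocol Appendix A). They cover part of the ground only: shift tables are for selected analytes and give no by-visit threshold counts, and Protocol 9.1.2 generally keeps clinically insignificant laboratory findings out of the adverse event record.

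A further objection is that the rule ignores the value, so a rising retest could replace a lower one. That is true relative to the first sample. It cannot push a single-analyte count above one based on the window's worst value.

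**Conclusion.** The point holds for the by-visit CK, ALT/AST and bilirubin threshold categories. Applied literally, Appendix A lets a below-threshold repeat displace the value that prompted it when the lag is shorter than twice the number of days the visit was early, or on a same-day repeat. It also drops an unscheduled elevation that lies farther from target than a normal scheduled value. Relative to any value above threshold in the window, these incidences can only be equal or too low.

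The size is unknown. The range from 7 of 15 visit days at a 1-day lag to none from 14 days rests on an assumed even spread of visits and describes displacement, not loss. Overall incidence is undefined in its source records and not shown to be wrong. The worst-shift, adverse event and event-of-interest tables are unaffected. The analysis is descriptive, so no error rate or power is involved, and a reading that the primary endpoint is compromised would go beyond the documents.

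**What to change.** In SAP 10.6.3, with a cross-reference in Appendix A, state that:

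1. By-visit CK, ALT/AST and bilirubin categories use the worst value among all central-laboratory records in the window, scheduled and unscheduled.
2. The overall incidence uses all such values after the first dose in the extension study.
3. The combined ALT/AST, bilirubin and ALP row is evaluated on every sample, with components from the same sample or a stated concurrent interval. A subject counts if any sample qualifies. Worst values from different dates should not be combined.
4. The nearest-record rule stays for means, changes and lipids.

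The cost is a few sentences and slightly more programming. No new data are needed and no clinical rule changes. Some by-visit incidences will be slightly higher.

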Appendix B. Common Terminology Criteria for AEs (CTCAE)

Refer to the NCI Common Terminology Criteria for AEs (CTCAE) for AEs and lab shift grading and information. The CTCAE is available at the following link:

<http://evs.nci.nih.gov/ftp1/CTCAE/About.html>

Appendix C. Framingham Risk Score (FRS)

Method to calculate the Framingham Risk Score (FRS):

The β coefficients given in the two tables below are used to compute a linear function. The latter is corrected for the averages of the participants' risk factors (mean) from the Framingham study, and the subsequent result is exponentiated and used to calculate a 10-year probability of HCHD after insertion into a survival function (Wilson et al).

The calculation is different for men and women, and use the following coefficients β_i , where i represents each of the independent variables. The values below are from the Framingham heart study

(<http://www.framinghamheartstudy.org/risk-functions/coronary-heart-disease/har-10-year-risk.php>).

t_chol = total cholesterol, hdl = HDL-C, sbp = systolic blood pressure, trt_htn = treatment for hypertension (if sbp > 120), smoker = current smoker

Men			Women		
Independent variable	Coefficient β_i	mean	Independent variable	Coefficient β_i	mean
ln(age)	52.00961	3.8926095	ln(age)	31.764001	3.9213204
ln(t_chol)	20.014077	5.3441475	ln(t_chol)	22.465206	5.3628984
ln(hdl)	-0.905964	3.7731132	ln(hdl)	-1.187731	4.0146369
ln(sbp)	1.305784	4.8618212	ln(sbp)	2.552905	4.8376494
trt_htn (spb>120)	0.241549	0.1180474	trt_htn (spb>120)	0.420251	0.142802
smoker	12.096316	0.335602	smoker	13.07543	0.3236202
ln(age)*ln(t_chol)	-4.605038	20.8111562	ln(age)*ln(t_chol)	-5.060998	21.0557746
ln(age)*smoker ¹	-2.84367	1.2890301	ln(age)*smoker ²	-2.996945	1.2519882
ln(age)*ln(age)	-2.93323	15.2144965			

¹ if age>70 then ln(70)*smoker

² if age>78 then ln(78)*smoker

The steps to determine the FRS is the same for men and women.

Men

For each subject:

1. Calculate $L_{\text{men}} = \beta_{\ln(\text{age})} * \ln(\text{age}) + \beta_{\ln(\text{t_chol})} * \ln(\text{t_chol}) + \beta_{\ln(\text{hdl})} * \ln(\text{hdl}) + \beta_{\ln(\text{sbp})} * \ln(\text{sbp}) + \beta_{\text{trt_htn}} * (\text{if trt_htn}) + \beta_{\text{smoker}} * (\text{if smoker}) + \beta_{\ln(\text{age}) * \ln(\text{t_chol})} * \ln(\text{age}) * \ln(\text{t_chol}) + \beta_{\ln(\text{age}) * \text{smoker}} * \ln(\text{age}) * (\text{if smoker}) + \beta_{\ln(\text{age}) * \ln(\text{age})} * \ln(\text{age}) * \ln(\text{age})$
2. Calculate $A_{\text{men}} = L_{\text{men}} - 172.300168$ (note: the value of 172.300168 was derived based on the mean columns in above table)
3. Calculate $B_{\text{men}} = \exp(A_{\text{men}})$
4. Calculate $P_{\text{men}} = 1 - 0.9402^{B_{\text{men}}}$
5. $\text{FRS}_{\text{men}} = P_{\text{men}} * 100$ (rounded to nearest integer)

Women

For each subject:

1. Calculate $L_{\text{women}} = \beta_{\ln(\text{age})} * \ln(\text{age}) + \beta_{\ln(\text{t_chol})} * \ln(\text{t_chol}) + \beta_{\ln(\text{hdl})} * \ln(\text{hdl}) + \beta_{\ln(\text{sbp})} * \ln(\text{sbp}) + \beta_{\text{trt_htn}} * (\text{if trt_htn}) + \beta_{\text{smoker}} * (\text{if smoker}) + \beta_{\ln(\text{age}) * \ln(\text{t_chol})} * \ln(\text{age}) * \ln(\text{t_chol}) + \beta_{\ln(\text{age}) * \text{smoker}} * \ln(\text{age}) * (\text{if smoker})$
2. Calculate $A_{\text{women}} = L_{\text{women}} - 146.5933061$ (note: the value of 146.5933061 was derived based on the mean columns in above table)
3. Calculate $B_{\text{women}} = \exp(A_{\text{women}})$
4. Calculate $P_{\text{women}} = 1 - 0.98767^{B_{\text{women}}}$
5. $\text{FRS}_{\text{women}} = P_{\text{women}} * 100$ (rounded to nearest integer)

Notes

- For men, if subject is > age 70, then use $\ln(70) * \text{smoker}$
- For women, if subject is > age 78, then use $\ln(78) * \text{smoker}$
- For dichotomous variables trt_htn and smoker use 1/0 to represent yes/no respectively
 - If a subject has $\text{sbp} \leq 120$ mmHg, then trt_htn is no

Calculated scores should match the interactive calculator

<http://hp2010.nhlbihin.net/atp/iii/calculator.asp?usertype=prof>

Appendix D. Lipid Modifying Background Therapy Intensity

Based on ACC/AHA guidelines:

	HIGH-INTENSITY STATIN THERAPY	MODERATE-INTENSITY STATIN THERAPY	LOW-INTENSITY STATIN THERAPY	Notes (classification of atypical doses)
Atorvastatin	40 mg or greater QD	10 mg QD up to less than 40 mg QD	Less than 10 mg QD	Atorvastatin 30 mg QD is Moderate intensity.
Rosuvastatin	20 mg or greater QD	5 – < 20 mg QD	less than 5 mg QD	Rosuvastatin < 5 mg QD is low intensity , Rosuvastatin 15 mg QD = moderate
Simvastatin	80 mg or greater QD	20-80 mg QD	< 20 mg QD	And Simvastatin > 40 and < 80 mg QD is moderate, Simvastatin 80 mg or greater QD = high, Simvastatin < 20 mg QD is low-intensity
Pravastatin		40 mg or greater QD	less than 40 mg QD	Pravastatin < 10 mg QD is low intensity
Lovastatin		40 mg or greater QD	less than 40 mg QD	Lovastatin 80 mg QD = moderate, Lovastatin 10 mg QD = Low-intensity
Fluvastatin		80 mg QD	less than 80 mg QD	Fluvastatin 10 mg QD = Low-intensity
Pitavastatin		≥ 2 mg QD	< 2 mg QD	

UNKNOWN-INTENSITY STATIN THERAPY if dose frequency is other or dose unit is other and therefore total daily dose in mg cannot be derived; NO STATIN THERAPY if subject does not use any statin at baseline.
